12.1.5. Electrocardiogram (ECG)

Six-lead ECGs will be performed after the subject has been resting in a supine position for at least 5 minutes. The ECG variables will include ventricular heart rate and the PR, QRS, QT, and QTcF intervals.

All abnormal ECGs will be interpreted by the Investigator as abnormal NCS, or abnormal CS in source documents. The standard intervals, any rhythm abnormalities, and the Investigator interpretation will be noted on the eCRF.

12.1.5.1. Drugs of Abuse and Alcohol

A urine drug screen will be conducted for the assessment of selected drugs of abuse (amphetamines, barbiturates, benzodiazepines, THC, cocaine, methadone, phencyclidine, opiates, 3,4-methylenedioxy-methamphetamine (MDMA), and oxycodone). A breathalyzer alcohol screen will be conducted.

12.1.5.2. Pregnancy Screen

A urine pregnancy test will be conducted for all women at Screening; thereafter, a urine pregnancy test will be conducted for women of child-bearing potential at all subsequent periods.

12.1.6. Columbia-Suicide Severity Rating Scale (C-SSRS)

Suicidality will be monitored during the study using the C-SSRS (Posner, 2011). This scale consists of a baseline evaluation that assesses the lifetime experience of the subject with respect to suicidal ideation and behavior, and a post-baseline evaluation that focuses on suicidality since the last study visit. The C-SSRS includes 'yes' or 'no' responses for assessment of suicidal ideation and behavior as well as numeric ratings for severity of ideation, if present (from 1 to 5, with 5 being the most severe).

The "Baseline/Screening" C-SSRS form will be completed at Screening (lifetime history and past 24 months).

12.2. Adverse Events and Serious Adverse Events

12.2.1. Adverse Event Definitions

12.2.1.1. Adverse Event (AE)

An AE is any untoward medical occurrence in a patient or clinical investigation subject administered a pharmaceutical product and that does not necessarily have a causal relationship with this treatment. An AE can therefore be any unfavorable and unintended sign (including an abnormal laboratory finding), symptom or disease temporally associated with the use of a medicinal (investigational) product whether or not related to the medicinal (investigational) product. In clinical studies, an AE can include an undesirable medical condition occurring at any time, including baseline or washout periods, even if no study treatment has been administered.

A TEAE is defined as an AE with onset after the first administration of any study drug or any worsening of a preexisting medical condition/AE with onset after the first administration of any study drug and through the follow-up phone call. The term study drug includes any study drug, a comparator, or a placebo administered in a clinical trial.

Laboratory abnormalities and changes from baseline in vital signs and ECGs are considered AEs if they result in discontinuation of study treatment, require therapeutic medical intervention or if the Investigator considers them to be clinically significant. Any abnormalities that meet the criteria for an SAE should be reported in an expedited manner.

All AEs that occur after any subject has signed the informed consent and throughout the duration of the study, whether or not they are related to the study, must be reported to the Medical Monitor.

Any AEs that are unresolved at the subject's last AE assessment in the study are followed up by the Investigator for as long as medically indicated, but without further recording in the eCRF. The Sponsor or its representative retains the right to request additional information for any subject with ongoing AE(s)/SAE(s) at the end of the study, if judged necessary.

12.2.1.2. Serious Adverse Event (SAE)

A serious adverse event is any untoward medical occurrence that at any dose:

- Results in death;
- Is immediately life-threatening;
- Requires in-patient hospitalization or prolongation of existing hospitalization;
- Results in persistent or significant disability or incapacity;
- Results in a congenital abnormality or birth defect.

An SAE may also be any other medically important event that, in the opinion of the Investigator may jeopardize the subject or may require medical intervention to prevent one of the outcomes listed above (examples of such events include allergic bronchospasm requiring intensive treatment in an emergency room or convulsions occurring at home that do not require an inpatient hospitalization).

All SAEs that occur after any subject has signed the ICF and throughout the duration of the study, whether or not they are related to the study, must be recorded on the SAE report form provided by NADS and Acclaro. Any SAE that is ongoing when the subject completes their final study visit, will be followed by the Investigator until the event has resolved, stabilized, or returned to baseline status.

A prescheduled or elective procedure or routinely scheduled treatment will not be considered an SAE, even if the subject is hospitalized. The site must document all of the following:

- The prescheduled or elective procedure or routinely scheduled treatment was scheduled (or on a waiting list to be scheduled) prior to obtaining the subject's consent to participate in the study.
- The condition requiring the prescheduled or elective procedure or routinely scheduled treatment was present before and did not worsen or progress, in the opinion of an Investigator, between the subject's consent to participate in the study and at the time of the procedure or treatment.

12.2.2. Relationship to Study Drug

The Investigator must make the determination of relationship to the study drug for each AE (not related or related). The following definitions should be considered when evaluating the relationship of AEs and SAEs to the study drug.

Not Related	An AE will be considered “not related” to the use of the study drug if there is not a reasonable possibility that the event has been caused by the study drug. Factors pointing towards this assessment include but are not limited to the lack of temporal relationship between administration of the study drug and the event, the presence of biologically implausible relationship between the product and the AE, or the presence of a more likely alternative explanation for the AE
-------------	--

Related	An AE will be considered “related” to the use of the study drug if there is a reasonable possibility that the event may have been caused by the product under investigation. Factors that point towards this assessment include but are not limited to a positive rechallenge, a reasonable temporal sequence between administration of the drug and the event, a known response pattern of the suspected drug, improvement following discontinuation or dose reduction, a biologically plausible relationship between the drug and the AE, or a lack of alternative explanation for the AE
---------	---

12.2.3. Recording Adverse Events

Adverse events spontaneously reported by the subject and/or in response to an open question from the study personnel or revealed by observation will be recorded during the study at the investigational site. The AE term should be reported in standard medical terminology when possible. For each AE, an investigator will evaluate and report the onset (date and time), resolution (date and time), intensity, causality, action taken, outcome, and seriousness (if applicable), and whether or not it caused the subject to discontinue the study drug or withdraw early from the study.

Intensity will be assessed according to the following scale:

- Mild: symptom(s) barely noticeable to subject or does not make subject uncomfortable; does not influence performance or functioning; prescription drug not ordinarily needed for relief of symptom(s)
- Moderate: symptom(s) of a sufficient severity to make subject uncomfortable; performance of daily activity is influenced; subject is able to continue in study; treatment (including but not limited to prescription drugs) for symptom(s) may be needed
- Severe: symptom(s) cause severe discomfort; symptoms cause incapacitation or significant impact on subject’s daily life; severity may cause cessation of treatment with study drug; treatment for symptom(s) may be given and/or subject hospitalized

It is important to distinguish between serious and severe AEs. Severity is a measure of intensity, whereas seriousness is defined by the criteria under Section 12.2.1.2. An AE of severe intensity may not necessarily be considered serious.

12.2.4. Reporting Serious Adverse Events

In order to adhere to all applicable laws and regulations for reporting an SAE(s), the study site must notify Acclaro or designee within 24 hours of the study site staff becoming aware of the SAE(s). The Investigator must complete, sign and date the SAE report form, verify the accuracy of the information recorded on the SAE report form with the corresponding source documents, and send a copy to Acclaro or designee.

Additional follow-up information, if required or available, should all be sent to Acclaro or designee within 24 hours of receipt on a follow-up SAE report form and placed with the original SAE information in the source documents.

Serious events occurring after the designated follow-up time for the study, should be reported to Acclaro or designee according to the timelines noted above only if the Investigator considers the SAE related to study drug.

Acclaro or designee is responsible for notifying the relevant regulatory authorities of certain events. It is the principal investigator's responsibility to notify the Ethics Committee (EC) of all SAEs that occur at his or her site. Investigators will also be notified of all suspected unexpected serious adverse reactions (SUSARs) that occur during the clinical study. Each site is responsible for notifying its EC of all SUSARs.

Appropriate personnel at NADS will unblind SUSARs for the purpose of regulatory reporting. The PI or designee will submit SUSARs (in blinded or unblinded fashion) to regulatory agencies according to local law.

12.3. Pregnancy

If a female subject becomes pregnant after first administration of study drug, pregnancy information must be collected, recorded, and submitted to Acclaro or designee within 24 hours of learning of the pregnancy. The female subject's participation in the study will be terminated.

Pregnancy in itself is not regarded as an AE unless there is a suspicion that a study drug may have interfered with the effectiveness of a contraceptive medication. The status of the pregnancy is not followed once participation in the study ends.

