Subjects will undergo initial driving simulator training and practice during the Screening period and will complete a practice drive on Day 1 of each treatment period.

Subjects will be discharged from NADS on the afternoon of Day 2 of each treatment period approximately 5.33 hours post-dose, provided they are medically stable for discharge in the opinion of the Investigator. The subject will not be able to drive themselves home and will have transportation arranged.

After a washout of at least 7 days, but no more than 10 days, between administration of the last dose in one period and administration of the first dose in the next period, subjects will be readmitted to NADS on Day 1 of Period 2 and receive study drug according to the assigned

treatment schedule. All study assessments will remain the same as in Period 1. The same process will be repeated for Period 3.

Seven days (± 2 days) after discharge from Period 3, subjects will receive a follow-up/end-of-study phone call from the site to evaluate the presence of any AEs and collect any new concomitant medication/procedure information.

The schedule of assessments is provided in [Table 1](#). The following regimens will be assessed:

- Cannabis (inhaled) on Day 2
- Alprazolam 0.75mg on Day 2
- Placebo on Day 2

Subjects will receive 0.75mg of alprazolam (over-encapsulated) or matching placebo capsule 40 minutes prior to administration of inhaled cannabis or matching placebo inhalation/vaporizer on Day 2 of each Treatment Period. Matched placebo tablets and/or vaporizers will be administered as necessary to maintain the blind across the 3 treatment regimens.

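### Section 12.3 stops following a pregnancy once participation ends, so no planned step collects the outcome of a known exposed pregnancy (low severity)

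*Combined protocol and SAP*

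**What the plan says.** Section 12.3 applies to a woman who "becomes pregnant after first administration of study drug". Pregnancy information must be "submitted to Acclaro or designee within 24 hours of learning of the pregnancy", and the woman's "participation in the study will be terminated". The section closes with "The status of the pregnancy is not followed once participation in the study ends".

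It also limits when a pregnancy counts as an adverse event: "Pregnancy in itself is not regarded as an AE unless there is a suspicion" that study drug interfered with contraception.

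Section 12.2.1.2 includes among the serious adverse event criteria "Results in a congenital abnormality or birth defect". Section 12.2.4 deals with serious events arising after the designated follow-up time. These go to Acclaro or designee "only if the Investigator considers the SAE related to study drug".

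The last planned contact (Section 7.1) is a phone call 7 ± 2 days after Period 3 discharge, made "to evaluate the presence of any AEs and collect any new concomitant medication/procedure information". Section 8.3 gives a withdrawn subject an early-termination contact and keeps the follow-up call on its schedule.

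**The concern.** The plan treats pregnancy exposure as a risk up to the moment it happens. Section 8.1 asks women of childbearing potential for two contraceptive regimens or abstinence. Section 12.1.5.2 tests them at every period, Section 8.2 excludes pregnancy at any admission, and Section 12.3 requires a 24-hour report. Follow-up is then switched off before there is any outcome to record. The plan names a birth defect as serious but contains no step by which the site would learn of one.

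What is at stake is one item of the safety record, the outcome of a pregnancy already known to have been exposed to study drug. Section 12.3 is an affirmative instruction, so a site that follows the protocol would not ask.

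**Working it through.** **1. The plan's own timeline.** The synopsis gives about 42 days of participation. Its components are 14 days of screening, three 2-day periods, two washouts of at least 7 days and a call about 7 days after discharge: 14 + 3×2 + 2×7 + 7 = 41 days, which agrees with the stated figure.

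**2. First dose to last call, subject completing Period 3.** Inputs from Section 7.1: doses are 7 to 10 days apart, discharge is on the dosing day, and the call is 5 to 9 days after Period 3 discharge.
- Minimum: 7 + 7 + 5 = 19 days.
- Maximum: 10 + 10 + 9 = 29 days.

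**3. Subject terminated earlier for pregnancy.** She has no Period 3 discharge, so the call has no stated anchor. Take the admission tests as falling on Day 1, one day before dosing. The Period 2 test is then on day 6–9 after first dose and the Period 3 test on day 13–19. Possible readings of the call date:
- From the Period 3 discharge she would have had: day 19–29.
- From her last actual discharge: day 5–9 if found at Period 2 (the call could then fall due before the test), or 7+5 to 10+9 = day 12–19 if found at Period 3.
- From an early-termination contact on the test day: 6+5 to 9+9 = day 11–18, or 13+5 to 19+9 = day 18–28.

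None of these goes beyond day 29.

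**4. Distance to birth.** Assume 266 days from conception to term birth (not in the documents). With conception on the day of first dose, the latest call precedes birth by 266 − 29 = 237 days. If the woman conceived up to 15 days before first dose and the Period 1 test missed it (assumed 14-day test lag, plus the day between test and dose), the gap is 266 − 15 − 29 = 222 days. The call could pick up an early loss reported as an adverse event, but not a birth outcome.

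**5. Other routes in the protocol.**

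| Route | Condition | What it leaves out |
|---|---|---|
| 8.3, follow-up of subjects withdrawn for an adverse event | The pregnancy counts as an adverse event | Any pregnancy without suspected contraceptive interference |
| 12.2.1.1, unresolved adverse events followed as medically indicated; sponsor may ask for more | Same | Same; no further eCRF recording |
| 12.2.1.2, SAEs ongoing at the final visit are followed | An SAE has already begun | An event that starts later |
| 12.2.4, late SAE reporting | The site hears of it and judges it related | Normal births; events unheard of or judged unrelated |

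None is a planned collection of the outcome.

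**6. Size.** Section 7.2 plans about 12 subjects, roughly half women, so up to about 6. The synopsis targets 6–8 completers, so as few as about 3 women. Assume all are of childbearing potential and take 1–10% pregnancies per woman-year (neither is in the documents).
- First dose to call: 3 × 19/365.25 × 0.01 = 0.0016, up to 6 × 29/365.25 × 0.10 = 0.048.
- Revealed by a Period 2 or 3 test (14 to 20 days' worth of conceptions, the interval from the Period 1 to the Period 3 test): 3 × 14/365.25 × 0.01 = 0.0012, up to 6 × 20/365.25 × 0.10 = 0.033.

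The upper ends pair the full 6 women with a 10% rate that sits poorly with two contraceptive regimens or abstinence. At 1%, the first-dose-to-call figure with 6 women is 6 × 29/365.25 × 0.01 = 0.005.

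**The case against.** The strongest reply is that this is a deliberate choice, stated in plain words. No objective, endpoint or analysis uses pregnancy outcome, and nothing in the documents requires follow-up to birth. By then dosing has stopped and no treatment decision depends on the answer. Exposure is at most one active cannabis dose and one alprazolam dose, in women who already use cannabis, so a single outcome could not establish cause. All of that stands, and it is why the point is low in severity. It does not give a reason for telling the site not to follow a pregnancy it already knows about.

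A reader might infer three stronger things that the documents do not support:
- **That the protocol contradicts itself.** Listing a birth defect as an SAE defines what is serious. It does not promise to look for one.
- **That a birth defect could never be reported, or that a pregnant subject is dropped without contact.** Sections 8.3, 12.2.1.1, 12.2.1.2 and 12.2.4 leave the conditional routes above, and Section 8.3 keeps an early-termination contact and a call.
- **That the 19–29 days applies to every subject.** It holds for one who reaches Period 3 discharge.

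**Conclusion.** The point holds as a low-severity, low-probability improvement to the safety record. Section 12.3 affirmatively ends follow-up, and no planned step replaces it. The 19–29 day figure rests only on the schedule. The gap of at least about 222 days to a term birth also needs the assumed gestation and test lag. The expected count, at most about 0.05 pregnancies, rests on the assumed number of women and pregnancy rate and should be read as an order of magnitude.

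Neither SDLP nor any other efficacy analysis changes. The case for acting rests on the low cost of the change, not on a likely harm.

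**What to change.** In Section 12.3, replace the closing sentence with: *The outcome of any known pregnancy exposed to study drug will be collected by phone or record, with the subject's consent, and reported to Acclaro or designee.*

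Also let the 24-hour report cover any known pregnancy exposed to study drug. The present trigger does not literally reach a woman who conceived shortly before first dose and tested negative at that admission. If she tests positive later, the exclusion at any clinic admission in Section 8.2 covers her removal but not the report.

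The cost is a protocol amendment with ethics approval (Section 16.1) and consent wording for later contact, if the consent form, which is not shown, lacks it. If a pregnancy is known, there are also one or two contacts and a safety file left open for some months after a study of about 42 days. If none occurs, there is no follow-up cost. The change does not improve detection: a pregnancy unknown at the last planned contact would still be missed unless the woman reports it.

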12.4. Overdose

An overdose is any dose of study treatment given to a subject or taken by a subject that exceeds the dose described in protocol. Overdoses are not considered AEs and should not be recorded as an AE on the CRF; however, all overdoses must be recorded on an Overdose form and sent to the sponsor or designee within 24 hours of the site becoming aware of the overdose. An overdose must be reported to the sponsor or designee even if the overdose does not result in an AE. If an overdose results in an AE, the AE must be recorded.

13. STATISTICS

A separate statistical analysis plan (SAP) will provide a detailed description of the analyses to be performed in the study. The SAP will be finalized and approved prior to database lock. Any deviations from or changes to the SAP following database lock will be described in detail in the clinical study report.

13.1. Data Analysis Sets

The Randomized Set is defined as all subjects who are randomized.

The Full Analysis Set (FAS) is defined as all randomized and treated subjects that have at least one primary efficacy measure (SDLP) in any treatment period.

The Safety Set (SS) is defined as all subjects administered at least one dose of any study drug.

The PK Set is defined as all subjects in the SS who have at least one collected blood sample from which a valid blood concentration can be measured.

13.2. Handling of Missing Data

Every attempt will be made to avoid missing data. All subjects will be used in the analyses, as per the analysis populations, using all non-missing data available. No imputation process will be used to estimate missing data.

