Subjects will be discharged from NADS on the afternoon of Day 2 of each period approximately 5.33 hours post-dose, provided they are medically stable for discharge in the opinion of the Investigator based on the criteria established by the medical monitor. The subject will not be able to drive themselves home and will have transportation arranged.

After a washout of at least 7 days and no more than 10 days between administration of the last dose in one period and administration of the first dose in the next period, subjects will be readmitted to NADS on Day 1 of Period 2 and receive study drug according to the assigned treatment schedule. All study assessments will remain the same as in Period 1. The same process will be repeated for Period 3.

Seven days (± 2 days) after discharge from Period 3, subjects will receive a follow-up/end-of-study phone call from the site to evaluate the presence of any AEs and collect any new concomitant medication/procedure information.

Figure 1. Study Design

The schedule of assessments is provided in [Table 1](#).

The following regimens will be assessed:

- Treatment A: cannabis (inhaled)
- Treatment B: alprazolam 0.75 mg PO
- Treatment C: placebo PO
- Subjects receive 1 tablet of alprazolam and/or matched placebo 40 minutes prior to administration of inhaled cannabis/or matching placebo on Day 2 of each treatment period.

Treatment Sequences

Sequence	1	2	3
1	A	B	C
2	B	C	A
3	C	A	B
4	A	C	B
5	B	A	C
6	C	B	A

Number of Subjects (planned): Approximately 12 subjects will be randomized and dosed to target 6 - 8 subjects completing the 3 treatments. Efforts will be made to randomize an approximately equal number of subjects by gender. Efforts will be made to randomize an approximately equal number of “low frequency” users (1-10 uses per month) and “high frequency” users (>20 uses per month).

Eligibility Criteria:

Inclusion

1. Subject understands and provides written informed consent prior to the initiation of any protocol-specific procedures.
2. Subject is able to comprehend and willing to comply with the requirements of the protocol.
3. Subject is a healthy male or female, 19 to 45 years of age, inclusive, at Screening.
4. Subject has a regular sleep pattern (usual bedtime between 21:00 and 00:00).
5. Subject has Score <10 on Epworth Sleepiness Scale at Screening.

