8.3. Subject Withdrawal Criteria

Subjects may withdraw from the study at any time for any reason. The Investigator may withdraw a subject from the study for any of the following reasons:

- The subject is unwilling or unable to adhere to the protocol
- The subject experiences an intolerable AE
- Other medical or safety reason, at the discretion of the Investigator and/or the Medical Monitor

If a subject is persistently noncompliant, the Investigator should discuss with the Sponsor the potential withdrawal of the subject. Any reasons for unwillingness or inability to adhere to the protocol must be recorded in the subject's eCRF, including:

- missed visits;
- interruptions in the schedule of study drug administration and/or assessments;
- non-permitted medications (Section 9.3.2);
- violation of other restrictions (Section 9.3.3).

Subjects who withdraw from the study due to an AE, regardless of Investigator-determined causality, should be followed until the event is resolved, considered stable, or the Investigator determines the event is no longer clinically significant.

Subjects who withdraw from the study for any reason should have an early termination (ET) visit/phone call and the follow up phone call should take place as scheduled. The Investigator must notify the Sponsor when a subject withdraws from the study for any reason. The reason must be recorded in the subject's case report form. A subject will be deemed lost to follow-up after attempts at contacting the subject have been unsuccessful.

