9.6. Subject Compensation

Subjects will be compensated for their time and effort. Subjects who complete all study procedures successfully will receive up to \$1100. For subjects that do not complete, prorated compensation will be provided as show below. For each study visit, there will be an incentive for completing one of the drives safely in the time allowed. This incentive compensation is \$25 per visit.

	Base	Incentive	Max Total
Screening	\$50		\$50
Visit 1	\$275	\$25	\$300
Visit 2	\$300	\$25	\$325
Visit 3	\$400	\$25	\$425
Total Base Pay			\$1025
Max Total Compensation			\$1100

Additionally, subjects will not be permitted to drive themselves after the study visits and must procure their own transportation. Based on historical costs, subjects will be reimbursed \$35 per trip to cover the expenses of a taxi or rideshare.

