13.5. Pharmacodynamic Analyses

All PD analyses will use the FAS Set.

The FAS will be used for the primary analysis. Summary statistics will be provided (mean, standard deviation, median, minimum, maximum) for each treatment. Figures will be provided for the within-subject difference scores by treatment and day as both a histogram and scatter plot. Data listings for driving simulator data will be provided.

SDLP data will be analyzed using a mixed model for repeated measures (MMRM) with fixed effects for sequence, period, and treatment and random effect for subject. A log-transformation of SDLP values to obtain normal distribution of data will be considered, if necessary. An unstructured covariance structure and Kenward-Roger degrees of freedom will be used. In the event an unstructured covariance structure fails to converge, a variance components covariance structure will be assumed. In addition to treatment effect, p-values for significance testing of period and sequence effects will be provided. Pair-wise comparisons of differences in means and two-sided 95% CIs on differences will be provided for all active treatments versus the placebo treatment.

The comparison of primary interest is cannabis versus placebo on Day 2 as a function of frequency of self-reported cannabis use. The statistical significance of alprazolam versus placebo ($p < 0.05$) comparison for SDLP is considered only to validate the experiment and having the ability to detect effects (i.e., assay sensitivity).

Formal statistical tests (when performed) will be 2-sided and tested at the $\alpha=0.05$ level of significance. Cannabis will be considered non-inferior to placebo if the two-sided upper 95% confidence limit on the difference in SDLP between that dose and placebo is less than 4.4 cm, and it can be concluded that the effect of cannabis on driving is less than that seen at 0.05% BAC, which is a level associated with increased crash risk. No adjustment to alpha levels will be made for either the comparison of alprazolam to placebo, or for secondary endpoints or analyses.

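### A drive lost to drug effect counts for nothing in the SDLP analysis, and no sensitivity analysis tests the non-inferiority conclusion against such losses

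*Combined protocol and SAP*

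**What the plan says.** Section 13.2 states the whole rule on this point: "All subjects will be used in the analyses, as per the analysis populations, using all non-missing data available. No imputation process will be used". It does not distinguish reasons for a gap.

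Under section 13.1 the Full Analysis Set is "all randomized and treated subjects that have at least one primary efficacy measure (SDLP) in any treatment period". A subject without a cannabis drive stays in the set through the other periods but supplies no cannabis value.

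Section 13.5 sets the main analysis: "SDLP data will be analyzed using a mixed model for repeated measures (MMRM) with fixed effects for sequence, period, and treatment". Subject enters as a random effect. The section's decision rule opens as follows: "Cannabis will be considered non-inferior to placebo if the two-sided upper 95% confidence limit on the difference in SDLP". The contrast is cannabis minus placebo, the bound is 4.4 cm, and passing is to mean an effect smaller than that of a 0.05% BAC. A supportive analysis applies McNemar and symmetry tests to within-subject SDLP differences. A non-significant, symmetric result there is to be read as showing no impairment of driving by cannabis.

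On completion, the Synopsis says: "Approximately 12 subjects will be randomized and dosed to target 6 - 8 subjects completing the 3 treatments". Section 8.3 allows withdrawal when "The subject experiences an intolerable AE", and asks for the reasons for missed visits and interrupted assessments to be recorded in the eCRF.

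The supplied text does not define how SDLP is handled when a drive is refused, not started or stopped early. It sets no minimum drive for a valid SDLP and plans no missing-data sensitivity analysis. Section 13 defers detail to a separate SAP, and section 11.1.1 defers drive-level detail to an operations manual. Neither is supplied.

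**The concern.** A subject who cannot begin the drive because of the drug shows the strongest form of the effect being measured. Under 13.2 that outcome is treated like a missed appointment. The mixed model is unbiased when drives are missing at random given the observed data. It is not unbiased when a drive is missing because of the impairment that would have been seen. The paired analyses lose the subject's cannabis-placebo pair altogether.

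The direction matters because 13.5 draws strong conclusions from a small difference: an effect below that of 0.05% BAC, or no impairment at all. Losing the worst cannabis drives moves the estimate towards both. Losing the worst alprazolam drives weakens the check that the scenario can detect impairment. Both results work against the primary objective in section 6.1, which is to validate the scenario.

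**Working it through.** **No figure to reproduce.** The documents give no SD, expected effect, power or sample-size derivation, so the size of the bias can only be shown under assumptions.

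**Inputs from the documents.** 12 subjects, three periods and six sequences (Synopsis; sections 7.2 and 7.3); two-sided 95% interval and 4.4 cm margin (13.5); no imputation (13.2).

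**Assumed inputs.** Within-subject SD 3 cm (also 4 cm), SD of individual cannabis effects 3 cm (also 4 cm), between-subject SD 5 cm, true mean difference 4.4 cm (exactly at the margin), one to three cannabis drives lost.

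**Illustration by hand.** Suppose ten observed pairs average 2 cm and two unobserved pairs would have averaged 12 cm. The true mean is (10 × 2 + 2 × 12) / 12 = 44 / 12 = 3.67 cm. The plan would report 2 cm.

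**Simulation.** SDLP was modelled with subject, period and treatment terms. Subject was fixed, as an approximation to the planned mixed model. The rule passes when estimate + t(0.975) × SE < 4.4 cm. The result depends on what is meant by the worst drives, so several versions are shown (n = 12, SDs 3 cm, true difference 4.4 cm):

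| Cannabis drives lost | One lost: false pass rate | Two lost: false pass rate |
|---|---|---|
| None (all drives observed) | 3.4% | 3.4% |
| Highest cannabis SDLP values | 6.2% | 9.3% |
| Subjects with the largest true cannabis effect | about 6% | 9.4% |
| Largest cannabis-placebo differences | up to about 9% | about 13-16% |
| Same number at random | about 3-4% | about 3-4% |

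Across versions and repeat runs, the range is about 6-9% with one lost and 8-16% with two.

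- **Estimate.** With the highest cannabis drives lost, the mean estimate falls from 4.36 cm to 4.00 cm (one lost), 3.64 cm (two) and 3.29 cm (three).
- **Interval.** The half-width grows slightly in that version, from 2.91 to 3.14 cm with three lost. The shift in the mean drives the result.
- **Other SD.** With SDs of 4 cm the pass rate goes from 2.8% to 6.6%, 9.8% and 14.3% for one, two and three lost.
- **Detecting an effect.** The chance of showing that cannabis raises SDLP falls from 81% to 64% with two lost (SDs 3 cm).
- **With an unfavourable value.** When the two subjects with the largest true effects have no cannabis drive, leaving the gap gives a mean estimate of 3.59 cm and a 9.4% pass rate. Using placebo plus the largest observed cannabis-placebo difference gives 4.82 cm and 3.2%, close to the 3.4% with all drives.

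**The case against.** The strongest reply is that nothing in the documents shows such losses will happen. Section 10.5 tells subjects to inhale only to a capacity free of dizziness, nausea, vomiting, panic or breathing difficulty. Section 5.2 cites tolerability at this THC level. Participants are current users, and those prone to simulator sickness are excluded. A subject who drives badly on cannabis and then withdraws has an observed cannabis drive, and the mixed model can treat the later gaps as missing at random. The separate SAP or the operations manual may hold a rule. All of this stands. It makes the bias conditional, but it does not supply a rule for the case where the condition is met.

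A reader might infer more than the text supports:

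- **That unfinished drives are dropped.** The text does not say so. A partial drive can yield an SDLP. Only a drive not started is certain to contribute nothing.
- **That 4 to 6 of 12 subjects are expected to be lost to the drug.** The Synopsis states a completer target over three visits and gives no reasons for non-completion.
- **That the payment term ("For each study visit, there will be an incentive for completing one of the drives safely in the time allowed") shows drives will go missing.** It is a $25 incentive. A slow drive or one with a crash still gives an SDLP.
- **That the interval narrows.** It need not, as shown above.
- **That the false pass rate reaches 18% with two lost.** A simple paired t interval that always loses the two largest differences gives this. That is a worst case and not the planned model.

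**Conclusion.** The concern holds in a conditional form. The rule in 13.2 ignores why a drive is missing, and the supplied text neither counts a drive lost to drug effect as an outcome nor tests the 13.5 conclusions against such a loss. If cannabis drives are lost for that reason, the estimated difference is too small and both favourable conclusions are easier to reach.

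At the margin, with 12 subjects and assumed SDs of 3 cm, the false non-inferiority rate goes from about 3% to about 6-9% with one worst drive lost and 8-16% with two. Random loss of the same number leaves it at about 3%, so the reason for the loss is what matters. The SDs, the true difference and the number lost are all assumptions. The documents do not support a claim that the bias will occur, only that the plan has no protection if it does.

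**What to change.** Amend sections 13.2 and 13.5, and reconcile them with the separate SAP and the operations manual:

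1. Before unblinding, classify every scheduled drive as completed, stopped early or not started, with the reason: drug effect, AE or inability to drive, or something unrelated. Build on the reasons already recorded under 8.3. State how SDLP is derived from a partial drive.
2. In the McNemar and symmetry analyses, count a drive lost to drug effect as a worsening above 4.4 cm for that treatment, in any arm.
3. Keep the no-imputation mixed model as the main estimate. Make the non-inferiority statement only if it also holds when those subjects' differences are set to the largest observed cannabis-placebo difference, or in a tipping-point analysis.

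Setting the lost differences at 4.4 cm would not be enough. In the simple paired set-up (SD 5 cm, n = 12, two largest differences lost) it moves the false pass rate only from 18.1% to 17.7%. The largest-observed value brings it to about 9%, which is better but not a full correction in that worst case.

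The cost is SAP wording, one CRF item per drive and a little more analysis, with no added subjects. If such drives occur, the non-inferiority statement becomes slightly harder to reach. If none occur, nothing changes.
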